3.16.3.1.1. Weeks 4, 8, 12, 16, 20, and 24 (Visits 14 Through 19)

During the study drug treatment period, patients will return to the study center once every 4 weeks (± 7 days) thereafter (relative to DoR/baseline) for administration of study drug and assessments until the end of the treatment period (week 24 or early withdrawal).

The following procedures/assessments will be performed before administration of study drug unless otherwise indicated:

- Perform urine pregnancy testing at weeks 4, 8, 12, 16, 20, and 24 or early withdrawal
- Perform hematology tests (CBC with differential) at weeks 4, 8, 12, 16, 20, and 24 or early withdrawal
- Perform serum chemistry tests (weeks 12 and 24 or early withdrawal) (a sample for CPK measurement only will also be collected on weeks 4, 8, 16, and 20).
- Perform brief physical examination at weeks 4, 8, 12, 16, 20, and 24 or early withdrawal
- Perform vital signs measurements (includes systolic and diastolic blood pressure, pulse, body temperature, and respiratory rate) at weeks 4, 8, 12, 16, 20, and 24 or early withdrawal
- Measure height and weight (week 24 or early withdrawal) for patients 12 to <18 years of age
- Measure weight (week 24 or early withdrawal) for adult patients
- Perform ECG (week 24 or early withdrawal)
- Perform adverse event inquiry
- Complete asthma-specific tests
 - Provide and collect PEF meter (week 24 or early withdrawal)
 - Provide/collect electronic asthma control diary; reinforce diary and PEF compliance (weeks 4, 8, 12, 16, 20, and 24 or early withdrawal)
 - OCS reduction attempts (weeks 4, 8, 12, 16, and 20)
 - Pre-bronchodilator spirometry (weeks 4, 8, 12, 16, 20, and 24 or early withdrawal)
 - Post-bronchodilator spirometry (weeks 4, 12, 20, and 24 or early withdrawal)

- AQLQ +12 (weeks 4, 8, 12, 16, 20, and 24 or early withdrawal) (may be completed after study drug administration during the 1-hour observation period)
- ACQ-6 (weeks 4, 8, 12, 16, 20, and 24 or early withdrawal) (may be completed after study drug administration during the 1-hour observation period)
- Collect blood for asthma biomarker analysis (week 24 or early withdrawal)
- Assess CAEs and related health care utilizations
- Collect blood for serum reslizumab concentration determination (PK assessment) (weeks 4, 8, 12, 16, 20, and 24 or early withdrawal)
- Collect blood sample for immunogenicity assessment (weeks 4, 8, 12, and 24 or early withdrawal)
- [REDACTED]
- [REDACTED]

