- Complete EQ-5D (week 24 or early withdrawal) (may be completed after study drug administration during the 1-hour observation period)
- [REDACTED]
- Complete SGRQ (weeks 12 and 24 or early withdrawal) (may be completed after study drug administration during the 1-hour observation period)
- Record any concomitant medications
- Investigational product (IP) administration (weeks 4, 8, 12, 16, and 20)
- Assess any OCS withdrawal effects (based on investigator’s assessment)

Additionally, the following procedures/assessments will be performed during and after administration of study drug:

- Patients will be observed for 1 hour after study injection.
- Evaluation of injection site for reaction at approximately 1 hour after dosing using the injection site CRF. Clinically significant injection site reactions should be recorded as an adverse event.
- If, during post-study drug observation, the patient develops clinical symptoms, vital signs should be collected. The patient should be assessed for anaphylaxis/hypersensitivity reactions as detailed in Section 7.1.7.

Remind the patients that they will receive a post-injection symptom inquiry via the eDiary.

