5. TREATMENT OF PATIENTS

5.1. Drugs Administered During the Study

After successfully meeting entry criteria, eligible patients will be randomly assigned to study drug (110 mg of reslizumab or placebo) with stratification based on maintenance OCS dose of >10 mg or ≤10 mg and age (12 to <18 years of age or 18 years of age or older) at baseline, using IRT, which uses computerized central randomization. Study drug will be administered by qualified study personnel as sc injections in the upper arm(s) once every 4 weeks for a total of 6 doses.

The pre-filled syringe has a staked 27G 0.5-inch needle. Subcutaneous injections can be given at a 90° angle or at a 45° angle. The injection can be given at a 90° angle if 2 inches of skin can be grasped between the thumb and first finger. If only 1 inch of skin can be grasped, the injection should be done at a 45° angle. The sites where injections are given should be at least 1 inch away from each other. Product should be removed from the refrigerator and allowed to equilibrate at room temperature for 15 to 30 minutes before administration.

Study drug will be administered by qualified study personnel who will ensure that the study drug is administered in accordance with the protocol. The needle shields of the prefilled syringes contain natural rubber latex, which may cause allergic reactions; see exclusion criterion (p). Additional information regarding study drug can be found in the Pharmacy Manual.

A more detailed description of the reslizumab drug product is provided in Section 3.11.1. Study drug exposure will be measured and compliance to study drug administration will be monitored.

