2.1.4. Treatment Period

Patients continuing to meet eligibility criteria on the day of randomization (day 1, week 0) will be randomly assigned in a 1:1 ratio to receive placebo or reslizumab 110 mg once every 4 weeks

through week 20, followed by an EOT visit at week 24. Patients will begin treatment on day 1 after completing baseline assessments, and they will return to the research facility for outpatient visits every 4 weeks through week 24 (EOT visit) for safety, PK, PD, immunogenicity, and efficacy assessments as applicable.

During the treatment period, the patient will continue his/her usual non-OCS background asthma medication without change; the OCS dose will be tapered per protocol. The treatment period consists of the following:

- **Induction:** The minimally effective dose of OCS will be maintained, unchanged, during the first 4 weeks of the treatment period to allow sufficient time for any potential treatment effect to become established.
- **OCS reduction:** The minimally effective OCS dose will be reduced per protocol at scheduled clinic visits from the beginning of week 5 (ie, end of the induction period) through week 20, as long as all 5 criteria in [Table 2](#) are met and there are no clinical manifestations of adrenal insufficiency. These 5 eligibility criteria assure that the patient's asthma control is not significantly worsened compared to baseline. The last possible dose reduction can occur at week 20. The algorithm for OCS reductions during the treatment period is given in [Table 3](#). If the OCS dose could not be decreased, it should be held constant or may be increased to a previous level, at the investigator's discretion, until dose reduction criteria are met.
- **Maintenance:** OCS dose will be held stable from week 20 through EOT at week 24.

Table 2: Eligibility Criteria for Scheduled Oral Corticosteroid Reductions During the Treatment Period (Must Meet All)

1.	Forced expiratory volume in 1 second (FEV ₁) ≥80% of baseline ^a
2.	AM PEF ≥80% of baseline mean AM PEF on at least 5 of the 7 days preceding the visit
3.	Mean nighttime awakenings due to asthma requiring rescue inhaler over the preceding 7 days ≤150% increase over the baseline period
4.	Reliever bronchodilator inhaler use does not exceed 150% of the baseline inhaler use per 24 hours on more than 2 of the preceding 7 days
5.	No increase in OCS dose since the previous visit ^b

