4.5. Study Days and Visit Windows

Study days will be numbered relative to the first day of study drug administration. The start of treatment (day 1) is defined as the date on which a patient takes the first dose of study drug, as recorded on the study drug diary. Days will be numbered relative to study start (ie, ..., -2, -1, 1, 2, ...) with day 1 being the start of study drug and day -1 being the day before the start of study drug).

For safety-by-visit summaries, if there are multiple assessments at a post-baseline visit then the last non-missing assessment at that visit will be used for the analysis. This includes assessments at the scheduled and unscheduled visits.

‘Endpoint’ for safety analyses and summaries is the time point when the last observation was obtained during the treatment period. For patients who completed treatment in this study, the treatment period will be defined from the first dose of study drug to the end of treatment (week 24) visit. For patients who prematurely discontinue treatment, the treatment period will be defined from the first dose of study drug to the last dose of study drug + 4 weeks.

For efficacy-by-visit summaries, only the assessments at the scheduled visit will be summarized. The assessments at unscheduled visits will be listed. For the purpose of the efficacy analysis, assessments collected at an early termination visit will be considered as the next scheduled visit for that assessment if at least 3 but no more than 5 weeks elapsed since the date of the last medication intake.

Efficacy-by visit summaries will be presented on-treatment. In this context, ‘endpoint’ will be defined as the last observation obtained at a scheduled or qualified early termination visit during the treatment period. For patients who completed treatment in this study, the treatment period will be defined from the first dose of study drug to the end of treatment (week 24) visit. For patients who prematurely discontinue treatment, the treatment period will be defined from the first dose of study drug to the last dose of study drug + 4 weeks.

For selected variables, additional sensitivity analyses may be presented utilizing all data collected over the entire course of the study including data collected after withdrawal for patients who prematurely discontinue from treatment. In this context, ‘endpoint’ will be defined as the last observation obtained at any post-baseline scheduled or qualified early termination visit.

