6.4. Other (and Exploratory) Efficacy Variable(s) and Analysis

As described previously in Section 4.5, an on-treatment approach will be adopted as the primary analysis for the efficacy variables assessed by-visit. In this analysis, the treatment period will be defined from the first dose of study drug to the end of treatment (week 24) visit for patients who completed treatment and from the first dose of study drug to the last dose of study drug (+4 weeks) for patients who discontinued treatment early. Measurements collected outside of these defined timeframes will be excluded from the analyses and endpoint will be defined within these timeframes. All results will be included in the patient listings. For selected key variables, additional sensitivity analyses may also be performed in which all post-baseline measurements collected during the study will be included and endpoint will be defined within this extended timeframe.

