6.4.9.2. Analysis

Compliance with the daily diary assessments will be derived for each patient as an additional measure of protocol adherence. A diary compliant day will be defined as a day with non-missing values for all diary assessments, including AM/PM asthma symptom score, AM/PM reliever use, AM/PM PEF, and nighttime awakenings. Diary compliance will be derived as a percentage over the treatment period:

- $\text{Diary compliance (\%)} = 100 \times (\text{total number of diary compliant days} / \text{total number of days during the treatment period})$

The treatment period for diary compliance extends from the first day of study drug to the last day of study drug. Note that, in this analysis, missing data will be treated as non-compliant (eg, if compliance cannot be assessed for a given day due to missing data, then the day will not be counted as a diary compliant day).

PEF measurements collected in the morning and in the evening will be summarized separately. Asthma symptoms collected in the morning and in the evening will be summed to derive a total

daily symptom score. Total reliever use will be derived as the sum of the morning and evening counts.

A weekly average of the daily diary measures (AM/PM PEF, total asthma symptom score, and total reliever use) will be derived (see [Table 6](#) for the definition of analysis days for diary data). The average will be calculated as the sum of all values divided by the number of non-missing assessments. There will be no imputation of missing data. At least 4 of the 7 measurements need to be recorded for a week to be included in the analysis; otherwise the week will be treated as missing.

Nighttime awakenings will be derived and analyzed as a percentage over the treatment period, derived as:

$$\text{Awakening-free nights (\%)} = 100 \times (\text{total number of awakening-free nights} / \text{total number of days during the treatment period})$$

The treatment period is defined in [Section 6.4](#). Note that missing data will be treated as non-responders in this analysis (eg, if response for nighttime awakenings is missing for a given day, then the day will not be counted as an awakening-free night).

Summary statistics of actual values and change from baseline to each week will be provided by treatment group.

Analysis of the change from baseline to each week will use a similar MMRM model as described in [Section 6.4.3.2](#) with the exception of inclusion of sex and height in the model.

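### As written, the diary-compliance period stops at the last injection, so it leaves out weeks 20 to 24 for completers and shrinks to one day after a single dose

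*SAP*

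**What the plan says.** SAP 6.4.9.2 defines a compliant day as one on which every diary item is present. It then says: "Diary compliance will be derived as a percentage over the treatment period". The subsection gives this statistic its own window: "The treatment period for diary compliance extends from the first day of study drug to the last day of study drug".

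The dosing schedule fixes where that window ends. Protocol 5.1 has study drug given "once every 4 weeks for a total of 6 doses", and SAP 2.1.4 has dosing "through week 20, followed by an EOT visit at week 24". SAP 4.5 ties the day count to injections: "Study days will be numbered relative to the first day of study drug administration".

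The diary continues past the last injection. Protocol 3.16.3.1.1 lists diary collection at every treatment visit up to week 24 or early withdrawal, and SAP Table 6 numbers treatment diary days up to day 167.

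For the other efficacy variables, SAP 6.4 defines the treatment period as running "from the first dose of study drug to the end of treatment (week 24) visit for patients who completed treatment", and to 4 weeks after the last dose for those who stop early. The awakening-free nights formula, also in 6.4.9.2, refers back to that definition.

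**The concern.** With an injection every 4 weeks, the last day of study drug is most naturally the date of the last injection. Where the SAP means a longer period (3.1, 3.2, 4.5, 6.3, 6.3.3.2, 6.4, 6.4.2.2, 7.1, 7.2), it names the week-24 visit or adds 4 weeks to the last dose. The compliance sentence does neither, and nothing in the SAP defines its end point differently. A programmer following it would stop at the last injection.

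Two things follow. The compliance figure says nothing about diary keeping after week 20. It also sits beside an endpoint from the same diary that does cover those weeks and treats a missing night as not awakening-free. A reader who uses compliance to judge how far missing entries drive the awakening-free result would be looking at a shorter window than the one analysed. For patients who stop early, the window loses the 4 weeks of on-treatment time that the SAP allows elsewhere.

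**Working it through.** **Plan's own figures first.** Injections at weeks 0, 4, 8, 12, 16 and 20 make 6 doses, as Protocol 5.1 states. Diary days to week 24: 24 × 7 − 1 = 167, as in SAP Table 6.

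**Completers.** The nominal day of week w is 7w + 1.
- Last injection: 7 × 20 + 1 = day 141. Literal denominator: 141 days.
- Week-24 visit: 7 × 24 + 1 = day 169. The SAP 7.2 duration for completers (visit date − first dose date + 1) is 169 days.
- Left out: 169 − 141 = 28 days; 28/169 = 16.6%.
- On the Table 6 scale: 167 − 141 = 26 diary days; 26/167 = 15.6%.
- With the ±7-day visit windows: from 162 − 148 = 14 days (14/162 = 8.6%) to 176 − 134 = 42 days (42/176 = 23.9%).

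**Early discontinuers.** For k doses on schedule, the literal denominator is 28(k − 1) + 1. The SAP 7.2 duration (last dose − first dose + 29) is 28(k − 1) + 29.

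| Doses | Literal days | SAP 7.2 days | Share left out |
|---|---|---|---|
| 1 | 1 | 29 | 96.6% |
| 2 | 29 | 57 | 49.1% |
| 3 | 57 | 85 | 32.9% |
| 4 | 85 | 113 | 24.8% |
| 5 | 113 | 141 | 19.9% |

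**Two figures from one diary.** Take a completer with every entry to day 141 and none afterwards. Compliance is 141/141 = 100%. The awakening-free percentage cannot exceed 141/169 = 83.4% (141/167 = 84.4% on the Table 6 scale).

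**Size of any overstatement.** Let a be compliance to day 141 and b compliance in the 28 days after it. The literal rule reports a. The full-period figure is (141a + 28b)/169, so the difference is (28/169)(a − b) = 0.166(a − b). The documents give neither a nor b, so these values are assumptions:
- a = b: no difference.
- a = 85%, b = 65%: (141 × 85 + 28 × 65)/169 = 81.7%, a difference of 3.3 points.
- a = 100%, b = 0%: 16.6 points, the maximum.
- b above a: the literal rule understates compliance.

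**The case against.** The best defence is that this is loose drafting. The change table in SAP Section 10 (Table 14) lists 6.4.9.2 among the sections using the common definition, which ends at the week-24 visit or at last dose + 4 weeks. The sponsor may therefore have meant that window here too. This stands as evidence of intent. However, the entry could equally refer to the awakening-free formula, and the current compliance sentence does not apply the common definition.

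The second defence concerns consequence, and most of it stands. The SAP presents compliance as a supplementary indicator of adherence to the protocol. It has no threshold, enters no model or test, and is not among the per-protocol exclusions in SAP Table 5. Late gaps are dealt with where they affect results: weekly means need at least 4 of 7 measurements, and missing nights count against awakening-free nights. Different denominators for two statistics are not in themselves an error.

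Because weeks 20 to 24 are also the maintenance period, a reader might infer that the gap touches the primary endpoint. The documents do not support that. Under SAP 6.2.1 the maintenance dose is prescribed prednisone from the CRF, and loss of control rests on FEV₁, ACQ-6 and exacerbations. The diary may inform the investigator's judgement of an exacerbation, but the compliance percentage does not. The diary-based criteria in SAP Table 2 apply at dose-reduction visits, the last at week 20, and the literal window covers that whole stretch.

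**Conclusion.** The point holds as a minor error in a stated rule. Taken literally, it omits 28 of 169 days (16.6%) for a completer on the nominal schedule, or 26 of 167 Table 6 diary days (15.6%), and leaves a 1-day denominator after a single dose. This rests on reading the end of the window as the last injection date, which is the natural reading for a 4-weekly injection.

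The effect is confined to a descriptive adherence statistic. No primary or secondary result changes. It would be tempting to conclude that reported compliance will be too high, but the documents do not establish that. The direction and size depend on how diary entry changes after week 20, and the difference is zero if it does not change. The documents also give no estimate of how many patients would stop after one dose.

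**What to change.** Replace the window sentence in SAP 6.4.9.2 so that diary compliance uses the Section 6.4 treatment period, counted in Table 6 diary days:
- Completers: through the last Table 6 diary day before the week-24 visit (nominally day 167).
- Early discontinuers: through last dose + 4 weeks, or the day the diary or PEF meter is returned if that is earlier.

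Both qualifications matter. Counted in calendar days, the Section 6.4 period runs to day 169, two days beyond Table 6, and those days could not be scored as compliant on the Table 6 scale. Protocol 4.5.1 asks early stoppers to attend a discontinuation visit as soon as possible with the early-withdrawal evaluations, and Protocol Table 5 includes collection of the meter and diary at that visit. Without the return-date limit, days after the patient handed back the device would count as non-compliant.

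The cost is one SAP sentence and a small programming change, with no new data. Reported compliance may be slightly lower. Unless the awakening-free formula is also counted in Table 6 days, a 2-day difference in completers' denominators (169 against 167) would remain.

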2.3.3. Other Prespecified Efficacy Endpoints

The other efficacy endpoints are as follows:

- Time to first CAE
- Other clinic lung functions including the following:
 - Pre-bronchodilator FEV₁: change from DoR/baseline to weeks 4, 8, 12, 16, 20, and 24 or early withdrawal
 - Post-bronchodilator FEV₁: change from DoR/baseline to weeks 4, 12, 20, and 24 or early withdrawal
- Ambulatory lung function: change in morning (AM) and evening (PM) peak expiratory flow (PEF) from run-in baseline at each week through week 24 or early withdrawal
- Asthma Quality of Life (AQLQ) + 12 score: change from DoR/baseline to weeks 4, 8, 12, 16, 20, and 24 or early withdrawal
- ACQ-6 score: change from DoR/baseline to weeks 4, 8, 12, 16, 20, and 24 or early withdrawal
- Change in total inhalations of reliever bronchodilator medication (eg, SABA) (number of inhalations per 24 hours: day+night) from run-in baseline at each week through week 24 or early withdrawal
- Number of nighttime awakenings due to asthma over the 24-week treatment period
- Change in total asthma symptom score from run-in baseline at each week through week 24 or early withdrawal

- European Quality of Life 5-dimension health state utility index (EQ-5D) score: change from DoR/baseline to week 24 or early withdrawal
- St. George’s Respiratory Questionnaire (SGRQ) score: change from DoR/baseline to weeks 12 and 24 or early withdrawal

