3.1.3. Run-In Period

Patients whose minimal effective OCS dose remains between ≥ 5 mg and ≤ 40 mg of prednisone daily at the end of optimization may advance to run-in (for at least 2 weeks). During run-in, patients will continue to keep their daily asthma control diary and a PEF meter to perform daily self-monitoring of asthma symptoms while maintaining their minimally effective OCS dose and previous background asthma medications unchanged. The frequency of symptoms, use of inhaled reliever bronchodilator, nighttime awakenings due to asthma requiring rescue inhaler, and ambulatory lung function during the last 7 days of run-in will constitute the baseline level of control for analysis and the basis for OCS reduction algorithm to be used during the treatment period.

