Analysis of the percentage of awakening-free nights will be performed using an analysis of variance (ANOVA) model with fixed effects for treatment, age group, and OCS dose at baseline.

A line graph presenting the LS mean change from baseline over time (at each week) will be provided for morning PEF, evening PEF, total asthma symptom score, and total reliever use by treatment group.

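### Awakening-free nights: a missing diary night scores as an awakening and the run-in value is unused, so a true effect is diluted, the result depends on diary compliance, and precision is lost

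*SAP*

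**What the plan says.** Protocol 2.3.3 lists among the other efficacy endpoints: "Number of nighttime awakenings due to asthma over the 24-week treatment period". SAP 6.4.9.2 turns this into the percentage of awakening-free nights, with "total number of days during the treatment period" as the denominator. The rule for blanks is explicit: "Note that missing data will be treated as non-responders in this analysis", with the example that "if response for nighttime awakenings is missing for a given day, then the day will not be counted as an awakening-free night".

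For patients who stop study drug early, SAP 6.4 ends the treatment period 4 weeks after the last dose. For completers it ends at the week 24 visit.

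The model is an "analysis of variance (ANOVA) model with fixed effects for treatment, age group, and OCS dose at baseline". No run-in awakening value enters it, although Protocol 3.1.3 says that symptoms, reliever use, night-time awakenings and ambulatory lung function "during the last 7 days of run-in will constitute the baseline level of control for analysis". Protocol 4.4 (criterion d) requires at least 4 diary days in that week before randomization.

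The rest of the plan works differently:
- In the same SAP section, PEF, symptom score and reliever use are averaged over non-missing entries, with at least 4 of 7 needed per week. They are analysed by the MMRM of SAP 6.4.3.2, which keeps the baseline value as a covariate.
- SAP 4.4 says that all variables other than the categorical OCS reductions will use observed data only.

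**The concern.** In this percentage a blank diary night is arithmetically the same as a night with an awakening. The endpoint therefore mixes two things: how often patients woke, and how often they filled in the diary. If the arms differ in the second, the difference appears as an effect on the first. If they do not differ, a true effect is still reported as smaller than it is. The rule also contradicts SAP 4.4, so the SAP gives two answers for the same blank entry.

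Separately, a baseline measurement of the same quantity is available for practically every randomized patient and is left out of the model. That widens the confidence interval with nothing gained in return.

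**Working it through.** **Planning figure.** The documents give no power or effect size for awakening-free nights. The only figure borrowed here is the 76 patients per group planned for the primary endpoint (SAP 2.3: OR 2.63, alpha 0.05, 90% power, stated placebo distribution). It reproduces. The proportional-odds formula N = 12(1.960 + 1.282)² / {(ln 2.63)² × [1 − Σp̄³]} gives 149.4 in total, or 74.7 per group; power with 152 patients is 90.5%.

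**Effect of the missing-night rule.** Let p be the true awakening-free share and c the share of nights with an entry, with nights missing independently of awakenings. The expected SAP percentage in an arm is c × p. The expected difference, reslizumab (R) minus placebo (P), is cR·pR − cP·pP. Over a nominal 168 days, each blank night costs 1/168 = 0.6 points. The values of p and c below are assumptions.

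*Equal compliance, true difference 10 points (70% v 80%):* the rule gives c × 10, that is 9 points at 90% compliance, 8 at 80% and 7 at 70%. With no true difference it gives 0.

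*Unequal compliance, no true difference:* the rule gives p × (cR − cP).

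| Compliance gap | p = 80% | p = 90% |
|---|---|---|
| 0 points | 0 | 0 |
| 2 points | 1.6 | 1.8 |
| 5 points | 4.0 | 4.5 |
| 10 points | 8.0 | 9.0 |

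The sign follows the arm with better compliance.

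*Unequal compliance, true difference 10 points (70% v 80%):*
- placebo 85%, reslizumab 80%: 0.80 × 80 − 0.85 × 70 = 4.5 points;
- placebo 80%, reslizumab 85%: 0.85 × 80 − 0.80 × 70 = 12.0 points.

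**Simulation check.** Settings: 76 per arm, 168 nights, 2,000 runs per scenario, compliance varying between patients, nights missing at random, stratification factors left out.
- With no true effect, the SAP rule rejected in 4.8% of runs at equal 80% compliance, 13% at 85% v 80% and 38% at 90% v 80%. With recorded nights as the denominator, rejection stayed near 5% throughout.
- With a true effect of about 12 points, power under the SAP rule fell from 82% with full diaries to 73% at equal 80% compliance. With recorded nights it stayed at about 82%.

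**Early leavers.** Only nights up to 4 weeks after the last dose count, so at most 28 nights are exposed, and only if diary entries stop. Take a patient whose last dose is at week 8. By the SAP 7.2 duration formula the period is 56 + 29 = 85 days. If entries stopped on the day of that dose, 28/85 = 33% of the denominator would be blank.

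**Run-in value as covariate.** The residual variance is multiplied by 1 − ρ² and the standard error by √(1 − ρ²). No document gives ρ.

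| Assumed ρ | SE reduction | Worth of 152 patients if the covariate is omitted |
|---|---|---|
| 0.3 | 1 − √0.91 = 5% | 152 × 0.91 = 138 |
| 0.5 | 1 − √0.75 = 13% | 152 × 0.75 = 114 |
| 0.7 | 1 − √0.51 = 29% | 152 × 0.51 = 78 |

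**The case against.** The rule is explicit and prespecified, and it uses the same missing-as-nonresponder logic as the OCS response endpoints. The trial is double-blind, the diary is reinforced in both arms at every visit, and nothing in the documents suggests that compliance will differ by arm. A reader might infer that diary compliance does bias this comparison. The documents do not support that: a false difference needs unequal compliance, and without it the null is undisturbed. This stands, and it is why the range above starts at zero. It does not remove the dilution, nor the conflict with SAP 4.4.

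A reader might also infer that early discontinuers hand the diary back and then accumulate awakenings. Protocol 4.5.1 asks patients who stop study drug to go on with visits and assessments to week 24, and no section says that diary use ends with treatment. The exposure is therefore conditional as well as capped at 4 weeks.

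The recorded-nights denominator has its own weakness: if patients skip the diary because they slept badly, it is biased too. This also stands, and it is the reason to keep both versions.

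On the baseline, the run-in value is a yes/no item over 7 nights, possibly only 4, so it moves in steps of 14 points or more and its correlation with the outcome may be modest. The Amendment 01 summary also shows that the endpoint was moved away from change from run-in. That explains the absence of a change score. It does not argue against a covariate.

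Finally, SAP 6.4.9.2 derives diary compliance per patient, which would help a reader judge the rule. But that measure stops at the last day of study drug. With the last dose at week 20, about 28 of 168 nights (17%) fall outside it even for completers, and the SAP does not say that it is tabulated by arm.

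**Conclusion.** The point holds as a minor one. The missing-night rule departs from the handling of the other diary variables and from SAP 4.4. It shrinks a true difference by the compliance fraction when compliance is equal. When compliance is unequal, it adds or removes about 0.8 to 0.9 points per percentage point of gap, in whichever direction the gap runs. These sizes rest on assumed compliance and on 80% to 90% awakening-free nights; the documents give neither.

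Omitting the run-in value does not make the randomized comparison invalid, as a reader might infer. It costs a standard error reduction of about 5% to 29% at an assumed correlation of 0.3 to 0.7.

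Nor should this be read as a threat to the trial's main result. The endpoint is in the other-efficacy group, for which SAP 4.3 makes no multiplicity adjustment, and it feeds no primary or secondary conclusion.

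**What to change.** In SAP 6.4.9.2:
1. Replace the ANOVA by an ANCOVA with the same factors plus the run-in percentage of awakening-free nights as a covariate.
2. Use nights with a recorded response as the denominator, with a minimum-data rule; the 4-of-7 weekly rule in the same section could be carried over.
3. Keep the missing-as-awakening version as a prespecified sensitivity analysis, because nights may be missing on account of awakenings.
4. Tabulate diary compliance by arm over the same window as the endpoint.

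In SAP 4.4, align the general missing-data statement with whatever 6.4.9.2 then says, including the sensitivity version.

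The cost is a few lines of SAP wording before unblinding, one covariate and one extra table. No new data are needed.
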